### Study Design

This is an exploratory, prospective, randomized, cohort study to be conducted in adult participants with episodic migraine (EM) or chronic migraine (CM). Participants will be recruited from sites that can offer all therapeutic options. A total of 200 participants will be enrolled in the study. Participants will be classified as living with either EM or CM based upon their medical history. Within these strata, the participants living with EM will be randomized to eptinezumab or other advanced preventive medication (i.e., erenumab, fremanezumab or galcanezumab) in a 1:1 manner. Those experiencing chronic migraine will be randomized to eptinezumab, subcutaneous (SC) CGRPs, or Botox in a 3:2:1 manner. Participants who are randomized to a SC CGRP will be permitted to select treatment with the injectable of their choice (i.e., erenumab, fremanezumab or galcanezumab). Participant data will be collected at multiple time points throughout the study. The daily migraine status,

symptom data, and acute migraine medication usage will be collected daily via a study-specific smartphone application (app). QOL data and HRU data will be collected two ways, via the smartphone application and the site staff. QOL assessments include the EuroQol-5 Dimension-5 Level (EQ-5D-5L), Headache Impact Test (HIT-6), Good Day/Bad Day scale and the Migraine Disability Assessment (MIDAS). All PROs will be completed directly by the participants via the app, with the exception of the Infusion Satisfaction Survey (ISS), that will be completed via paper questionnaire. Participants will complete the EQ-5D-5L and Good Day/Bad Day scale on a weekly basis, the HIT-6 monthly, and the MIDAS every 3 months. HRU will be tracked via participant input into the app and site staff led interviews.

Participants will be trained to report any healthcare interactions into the app (e.g., office visits, urgent care visits, picking up prescription medication). In addition, the site staff will interview participants monthly to determine if any healthcare system interactions occurred. Several additional measures are planned to assess participant preferences regarding shared decision making and satisfaction with their treatment.

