## 2 Objectives

This exploratory study has multiple objectives within the overall aim to examine how eptinezumab compares to other advanced preventive medications in a real-world community setting. These objectives include exploring the comparative effectiveness on patient reported outcomes (PROs) including and healthcare resource utilization (HRU). In addition, we will assess participant preferences for shared decision making, participant satisfaction with their treatment and confidence in managing their own health. Specifically, the objectives of EVEC include:

1. **Patient-identified most bothersome symptom (PI-MBS):** This will be measured on a daily basis using the PI-MBS. Participant will select the symptom that they find most impairs her or him at the time of reporting and rate the severity of that symptom. The difference between randomization groups evaluated at 4, 12 and 24 weeks following randomization.
2. **Good day/Bad Day scale:** The participant will report the number of "good days" and "bad days" they had in the previous week on a weekly basis using the Good Day/Bad Day scale. The difference between randomization groups evaluated at 4, 12, and 24 weeks.
3. **EuroQol 5-Dimension, 5-Level Quality of life Scale (EQ-5D-5L):** The participant will complete the EQ-5D questionnaire on a weekly basis to indicate their preference for their current health state. The difference between randomization groups evaluated at 4, 12, and 24 weeks
4. **Health resource utilization:** The participant will report their use of health services and medications on a daily basis using the smartphone app. The difference over time between the randomization groups will be evaluated at 4, 12, and 24 weeks.

5. **6-item Headache Impact Test (HIT-6):** The participant will report the impact of headache on their quality of life using the six-item HIT-6 scale. This will be done each month. The difference in change over time between randomization groups will be evaluated at 4, 12, and 24 weeks.
6. **Migraine Disability Assessment (MIDAS):** The participant's perception of their degree of disability will be evaluated by the MIDAS scale. This will be measured quarterly. The difference in change over time between randomization groups will be evaluated at 12 and 24 weeks.

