**Panel 3: Post-Baseline eDiary Collected Assessments**

Assessments	Reporting Schedule				
	Daily	Weekly (a)	Monthly (b)	Quarterly (c)	Early Termination
Daily Headache Status Report: - Did they have a headache in the previous 24 hours? Y/N	X				X
If answer is “Yes” to “Daily Headache Status” then participants will be prompted to report their Daily Headache Symptoms: - What symptoms did they experience with the headache? - How do they rate the severity of the symptoms? - What was the most “bothersome” of the symptoms (i.e. PI-MBS)?	X				X
If answer is “Yes” to “Daily Headache Status” then participants will be prompted to report their Acute Headache Medication Usage: - What medication(s) did they take (if any) to relieve the headache? - How do they rate the effectiveness of the medication(s) taken?	X				X
If answer is “Yes” to “Daily Headache Status” then participants will be asked if they considered this headache to be a migraine.	X				X
If answer is “No” to “Daily Headache Status” then participants will be prompted to respond to the following: - Do they have any residual symptoms lingering between headaches? - Have they experienced any “warning” symptoms prior to a headache? - What degree of impact did each of these symptoms have?	X				X

Assessments	Reporting Schedule				
	Daily	Weekly (a)	Monthly (b)	Quarterly (c)	Early Termination
Healthcare Resource Utilization	X (d)				X
EQ-5D-5L		X			X
Good Day/Bad Day Scale		X			X
PSS			X		X
HIT-6			X		X
PAM-10				X	X
MIDAS				X	X
SDM-Q-9				X	X
TSQM				X (e)	X

(a) Weekly = every 7 days, Visit 2 date = Day 0 (b) Monthly = every 28 days, Visit 2 date = Day 0

(c) Quarterly = every 84 days, Visit 2 date = Day 0 (d) Will be assessed 3 times per week

(e) Assessed at Day 168 only

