We will assume that residuals are normally distributed, and we will also assume an unstructured covariance structure of the residuals. The Kenward-Roger approximation will be used to estimate standard errors. The hypothesis tested will be that the interaction term of treatment and week is significantly different from zero using a two-sided test at $p<0.05$. The population level summary will be the difference in mean EQ-5D score at weeks 1-4. The analysis will also be conducted for weeks 1-12 and 1-24. If the model fails to converge, then other covariance structures will be utilized.

HCRU (weeks 1-4, 1-12, and 1-24)

The difference in cumulative mean HCRU will be estimated using a negative binomial model. The analysis will be stratified by type of HCRU (i.e., outpatient, inpatient hospitalization, emergency department/urgent care visits, and migraine-specific medications such as triptans). Independent variables will include a treatment indicator (eptinezumab vs other advanced therapies) and a vector of covariates identified to be significantly different between treatment groups after randomization. The hypothesis tested will be that the treatment term is significantly different from zero using a two-sided test at $p<0.05$. The population level summary will be the relative difference in mean HCRU at weeks 1-4. The analysis will also be conducted for weeks 1-12 and 1-24. If there are a substantial number of observations with a value of zero HCRU, then a zero-inflated negative binomial model will be explored.

HIT-6 change from baseline score (month 1, 3, and 6)

The mean HIT-6 change from baseline score will be estimated using a mixed model for repeated measures (MMRM). The model will include the following independent variables:

- Month as a factor (Baseline month 0, month 1, month 3, and month n)
- Treatment indicator (eptinezumab vs other advanced therapies)
- Interaction of treatment and month (treatment*baseline...treatment*month 1...treatment*month n)

- A vector of covariates identified to be significantly different between treatment groups after randomization.

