18.6.2 Medication HCRU

Migraine medication HCRU (over-the-counter and prescription) will be ascertained based on the patient's reported medication use during the monthly follow-up visits in which the study coordinator reviews all reported medication use in addition to any unreported utilization. Reported counts of medications will be summed across weeks 1-4, 1-12, and 1-24 based on the reported start and discontinuation dates of the medication.

Medications will be classified as acute, or preventive stratified by drug class:

- Acute
 - Oral anti-CGRP
 - Triptans
 - Analgesics (opioids, non-narcotic, anti-inflammatory)
 - Barbiturate hypnotics
 - Ergots
 - 5-HT agonist
 - Isometheptene
 - Antiemetics
- Preventive
 - Anticonvulsants
 - Serotonin-norepinephrine reuptake inhibitor
 - Selective serotonin reuptake inhibitors
 - Tricyclic antidepressants
 - Antihistamines
 - Antihypertensives (angiotensin converting enzyme inhibitors, angiotensin receptor blockers, beta-blockers, alpha agonists, calcium channel blockers)

- NMDA antagonists
- Monoamine oxidase inhibitors

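### Acute-medication HCRU is counted from start and stop dates, so the tested count is insensitive to how often an as-needed drug is taken

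*SAP*

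**What the plan says.** SAP 18.6.2 takes medication HCRU from "reported medication use during the monthly follow-up visits in which the study coordinator reviews all reported medication use". The counting rule is: "Reported counts of medications will be summed across weeks 1-4, 1-12, and 1-24 based on the reported start and discontinuation dates of the medication". It applies to as-needed and regular drugs alike: "Medications will be classified as acute, or preventive stratified by drug class". The rule has no term for days of use or doses.

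SAP 11.2.2 analyses the result formally: "The difference in cumulative mean HCRU will be estimated using a negative binomial model". One of the strata is "migraine-specific medications such as triptans", and the treatment term is tested two-sided at 0.05 for weeks 1-4, 1-12 and 1-24.

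The protocol collects more than this count uses. Whenever a headache is reported, the daily eDiary asks "What medication(s) did they take (if any) to relieve the headache" (Protocol Panel 3). The HRU objective in Protocol section 2 reads: "The participant will report their use of health services and medications on a daily basis using the smartphone app". SAP 18.6, however, bases the HCRU analysis on the follow-up questionnaire and uses the eDiary entries only to look for inconsistencies.

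**The concern.** Preventive treatment can reduce the number of days on which acute drugs are taken without any drug leaving the list. A triptan kept for use when needed, with a start date before baseline and no stop date, contributes the same amount to the count whether it is used often or rarely. Two arms with similar lists but different acute use would then look alike. A reader could take that result as evidence that treatment makes no difference to acute medication use.

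No other endpoint fills the gap. The daily acute-medication report otherwise enters the SAP analyses only through the definitions of a headache day and a migraine day (SAP 3.5.1 and 3.5.2). Yet the protocol itself measures acute use in days per month when it sets the opioid and butalbital exclusion (section 5.3) and describes medication overuse (section 5.4).

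**Working it through.** **No figure to reproduce.** The documents give no rate, effect size or power for medication HCRU. SAP 15.1 says that good preliminary data on these outcomes are lacking. The use rates below are therefore assumptions, and the comparison is between arms.

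**Step 1: what the rule can count.** SAP 18.6.2 does not define the unit of a count. There are three possible readings.
- Drugs on the list in the window: 1 per listed drug, whatever the use.
- Days from start to stop within the window: 28, 84 or 168 for a drug listed throughout, whatever the use.
- One dated record per intake: this would follow use, but neither document describes such a record.

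The follow-up questionnaire (Protocol Appendix XVI) does not supply the missing information. Its only medication entry is a change in prescription drugs, which is passed to the concomitant-medication form. It has no field for days or doses. SAP 18.6.1, by contrast, places medical HCRU by the date of each use, so it does count events.

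**Step 2: one worked comparison.** Assume one triptan listed throughout in both arms, with 4 v 7 use-days per 28 days.

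| Window | List count | Start-to-stop days | Use-days | Use-day ratio |
|---|---|---|---|---|
| Weeks 1-4 | 1 v 1 | 28 v 28 | 4 v 7 | 0.57 |
| Weeks 1-12 | 1 v 1 | 84 v 84 | 12 v 21 | 0.57 |
| Weeks 1-24 | 1 v 1 | 168 v 168 | 24 v 42 | 0.57 |

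**Step 3: a range.** Assume 10 use-days per 28 days in the reference arm (60 over 24 weeks), 100 per arm (SAP 15.1), and negative binomial dispersion k from 1.0 down to 0.3. Approximate power is Φ(|ln RR|/SE − 1.96), where SE² = (1/μ1 + k)/100 + (1/μ2 + k)/100.

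For example, take a 30% reduction with k = 0.6. Then μ1 = 60, μ2 = 42, and SE² = (0.0167 + 0.6)/100 + (0.0238 + 0.6)/100 = 0.0124, so SE = 0.111. With |ln 0.70| = 0.357, 0.357/0.111 ≈ 3.20 and power = Φ(1.24) = 0.893.

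| True reduction | Use-days, week 24 | Use-day ratio | Power, k = 1.0 to 0.3 | List-count ratio |
|---|---|---|---|---|
| 20% | 60 v 48 | 0.80 | 0.35 to 0.80 | 1.00 |
| 30% | 60 v 42 | 0.70 | 0.70 to 0.99 | 1.00 |
| 40% | 60 v 36 | 0.60 | 0.95 to above 0.99 | 1.00 |
| 60% | 60 v 24 | 0.40 | above 0.99 throughout | 1.00 |

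With equal lists, the test on the list count rejects about 5% of the time, the nominal error rate, whatever the true reduction.

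**Step 4: does an offset for reported days deal with missing diary days?** Only if use on missing days resembles use on reported days. Assume 4 use-days in 20 reported days, with all 8 missing days also use-days. The offset implies 28 × 4/20 = 5.6 use-days per 28, against a true 4 + 8 = 12. SAP 18.15.1 gives reason to expect this direction of error, since it assumes that patients do not complete the eDiary during a migraine.

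**The case against.** The strongest reply is that the rule is underspecified rather than wrong. The unit is undefined, and the source is a coordinator's review of all reported medication use. That point stands as far as it goes, but both natural readings ignore frequency, and the one reading that would not needs records that the documents do not describe.

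The count is also not fixed. It changes when an acute drug is started, stopped or replaced, and medication changes are recorded at every visit (SAP section 8). A reader might infer that the outcome cannot respond to better prevention at all. The documents do not support that: it is insensitive to frequency of use, not inert.

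The illustration builds in equal drug lists and invented use rates. That is correct, so it shows the mechanism and not an expected effect.

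SAP 18.6 gives a reason for preferring the follow-up data: they include use that the participant did not enter in the eDiary. This trade-off is real, and the fix has to carry it. It does not rescue the count, because a more complete list of drugs still says nothing about how often they are taken.

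**Conclusion.** The concern holds for the acute part of medication HCRU. As planned, the tested count responds only to drugs joining or leaving the list. Where lists are alike in the two arms, it gives a ratio of 1.00 against use-day ratios of 0.40 to 0.80 over the assumed range of reductions, and 0.57 in the 4 v 7 example. These sizes rest on assumed use rates, assumed dispersion and equal lists.

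A reader might also infer that the HRU objective cannot be answered. The documents do not support that. The outpatient, inpatient and emergency/urgent-care strata count dated events and are unaffected. This is one stratum of one exploratory endpoint, in a study that the protocol (section 3.3) says has no primary objective. The cost is a potentially misleading null on acute medication use. The change should be made because better data are already being collected.

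**What to change.** In SAP 18.6.2, define acute-medication HCRU as the number of eDiary days with acute medication use, by drug class, in weeks 1-4, 1-12 and 1-24. Fit the negative binomial model of SAP 11.2.2 with log(reported eDiary days) as offset, counting only reports valid under SAP 18.1. Use-days cannot exceed reported days, so check that the fitted values respect that limit. Keep the start/stop count for preventives, and as a description for acute drugs. State its unit.

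Add a sensitivity analysis for missing diary days that is consistent with SAP 18.15.1. For example, prorate weeks with at least 4 reported days and treat missing days as use-days in weeks with fewer than 4. Days filled in this way should enter both the count and the offset. State whether the rule continues after withdrawal.

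The cost is a change of derivation and some programming, with no new data collection. There are three limits to report with the result. Use-days depend on diary completion. They are captured only on days when a headache is reported, so a drug taken at warning symptoms on a headache-free day is missed. They also omit use found only at the monthly review; comparing the drugs named in the eDiary with the monthly list would show how much. The item supports days of use by class, not necessarily doses.

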#### **Exclusion Criteria**

1. The participant has previously been enrolled in this study.
2. The participant is a member of the study personnel or of their immediate families or is a subordinate (or immediate family member of a subordinate), to any of the study personnel.
3. The participant has a history of severe drug allergy or hypersensitivity, or known hypersensitivity or intolerance to either eptinezumab, erenumab, fremenezumab, galcanezumab or their excipients.
4. The participant has previous history of use of any of the study drugs (i.e. eptinezumab, Botox, erenumab, fremenezumab or galcanezumab). Participants who have used oral

CGRP inhibitors atogepant or rimegepant for prevention are also excluded. Note that only previous Botox use for treatment of migraine is exclusionary. Prior use of Botox for cosmetic purposes is allowed. Participants with a history of acute use of rimegepant or ubrogepant (but not for prevention) are permitted to enroll.

5. The participant has a diagnosis of CM and has hypersensitivity to botulinum toxin preparation or to any of the components in the formulation.
6. The participant has used opioids or butalbital-containing products greater than 4 days per month in the last month.
7. The participant is pregnant, <6 months post-partum, or breastfeeding.
8. The participant has a disease or takes medication that could, in the investigator's opinion, interfere with the assessments of safety, tolerability, or efficacy, or interfere with the conduct or interpretation of the study.
9. The participant is, in the investigator's opinion, unlikely to comply with the protocol or is unsuitable for any reason.

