## 6 Investigational Medicinal Products

### 6.1 Treatment Regimen

Participants will be randomized to their initial migraine prevention medication. Participants must receive the first dose of their allocated medication at the Baseline Visit (Visit 2). However, during the remainder of the study observation period, treatment choices will be based upon the treating clinician's judgement and the participant's preference (See Section 6.3.1 below for more details). No additional direction will be given by the CRO or the study sponsor. However, any participant wishing or needing to switch to an alternate medication outside of the study-specific guidelines for doing so, as described in Section 6.3.1, will need to be withdrawn from the study. Participants switching to an advanced preventive medication other than their initially assigned treatment in accordance with Section 6.3.1 will be permitted to remain in the study. There will be no restrictions on the use of other migraine related medications during the study period for acute or preventive treatment if those medications are prescribed by the participant's treating physician. However, products purchased with study-specific vouchers cannot be used for an off-label indication. Participants must meet the criteria for CM at baseline in order to be randomized to onabotulinumtoxinA (Botox®). Any changes in migraine preventive medications, prescribed or OTC, will be reported in the smartphone application by the participant. The reason for any treatment change will be

---

investigated by the study coordinator and recorded in the CRF. Any adverse events identified as the cause of a medication switch (e.g. lack of efficacy) will be reported according to Section 10.3.

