18.6 HCRU (weeks 1-4, 1-12, and 1-24)

All-cause medical HCRU will include outpatient physician visits, inpatient hospitalizations, urgent care visits, and emergency department visits. Medications (over-the-counter and

prescription) used for the acute relief and prevention of migraine will also be included. HCRU is reported by patients using the ePRO application on a daily basis and on the HCRU follow-up questionnaire, which is a comprehensive review of patient HCRU obtained by study coordinators during the monthly visits. Since the HCRU follow-up questionnaire contains more comprehensive information (i.e., patient reported HCRU and any that may not have been reported by the patient on the ePRO), the analysis will be based on the HCRU follow-up questionnaire. However, data reported in the ePRO and follow-up questionnaire will be compared to assess for inconsistencies. Missing values will not be imputed.

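### SAP 18.6.2 lists oral anti-CGRPs only as acute medication, so a gepant added for prevention drops out of the preventive medication count

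*SAP*

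**What the plan says.** SAP 18.6 defines the scope of medication resource use by purpose. Over-the-counter and prescription products are covered: "prescription) used for the acute relief and prevention of migraine will also be included". SAP 18.6.2 gives the counting rule, "Reported counts of medications will be summed across weeks 1-4, 1-12, and 1-24 based on the reported start and discontinuation dates of the medication", and the sorting rule, "Medications will be classified as acute, or preventive stratified by drug class". Two class lists follow. The first acute entry is "Oral anti-CGRP". The preventive list runs from anticonvulsants to monoamine oxidase inhibitors and has neither an oral anti-CGRP class nor a residual class.

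The protocol divides the same drugs by purpose. Exclusion criterion 4 in Protocol 5.3 says that participants who have taken oral "CGRP inhibitors atogepant or rimegepant for prevention are also excluded", and then: "Participants with a history of acute use of rimegepant or ubrogepant (but not for prevention) are permitted to enroll". That criterion concerns use before entry. For the period after baseline, Protocol 6.1 says: "There will be no restrictions on the use of other migraine related medications during the study period for acute or preventive treatment", provided that the treating physician prescribes them. Protocol 6.3.1 also allows gepants for acute relief in either arm.

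**The concern.** One drug class can serve two purposes in this trial, and the protocol relies on that difference at entry. The SAP's coding list does not carry it forward. If a programmer applies the list as written, a participant who adds a preventive gepant looks like one who has added an acute medication, and the preventive tally does not change.

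Adding a preventive while staying on the assigned drug can be a sign that the assigned drug is not enough. In a comparative-effectiveness study aimed partly at payers, that is information the medication breakdown should show. Here it would be absent from the preventive rows and could be read as acute use.

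**Working it through.** No arithmetic applies: the point rests on a classification list, and the plan states no figure to reproduce. The check is to set the passages side by side and pass example records through the rule.

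**Can the record occur?** Yes. Exclusion criterion 4 bars only previous preventive use, and Protocol 6.1 leaves other physician-prescribed preventives unrestricted during the study. SAP 18.6 puts preventive medication in scope.

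**Where does the list put it?** Oral anti-CGRPs appear in 1 of 8 acute classes and 0 of 8 preventive classes. Counting uses start and stop dates, and no step refers to the indication.

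**Example records**, each reported medication counting once:

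| Record after baseline | Class-list reading | Purpose first, then class |
|---|---|---|
| Topiramate added for prevention | preventive +1 | preventive +1 (anticonvulsant) |
| Rimegepant for attacks | acute +1 | acute +1 |
| Rimegepant for prevention | acute +1, preventive 0 | preventive by purpose, but no class to hold it |
| Atogepant for prevention | acute +1, preventive 0 | preventive by purpose, but no class to hold it |

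On the class-list reading, rows two and three are indistinguishable. On the purpose-first reading the acute count is right, but a preventive count built from the listed classes still omits rows three and four. Atogepant has a further uncertainty. SAP Appendix I names only rimegepant and ubrogepant under oral anti-CGRPs, so if those names define the class, atogepant falls in neither list. The omission from the preventive count is therefore common to these readings. The step into the acute count depends on the first.

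**Does Appendix I settle the matter?** No. It also lists the class only as acute medication, but as a screening covariate. That is reasonable there, because previous preventive users are excluded. It does not carry over to use after baseline.

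**Does another endpoint recover the record?** Only in part. SAP 11.2.1 defines switching as stopping the index therapy and starting a new one. A preventive gepant that replaces the index drug can appear there. One taken alongside it cannot.

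**Does it reach a tested comparison?** SAP 11.2.2 fits the resource-use model by type, and its medication stratum is "migraine-specific medications such as triptans". It does not call that stratum acute, and it names no preventive stratum. On that wording a gepant may belong in it whatever its purpose, so reclassification might leave the test unchanged.

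**The case against.** A reader might infer that the misfiling biases a between-arm test of acute medication, making the arm that needs more add-on prevention appear to use more acute drugs. The documents do not support that. SAP 11.2.2 defines no acute count for testing. The mention of triptans may hint at acute drugs, but that is inference. Any distorted ratio would also need assumed rates of preventive gepant use that differ between arms; at equal rates and equal true acute use, the ratio of acute counts would stay at 1.

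It can also be said that the sorting sentence already means purpose first. SAP 18.6 sets its scope by use, which favours that reading. This stands as a reason not to treat the acute miscount as certain. It does not supply the missing preventive class.

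Third, the information is not lost. Oral anti-CGRPs have their own row, so they are not merged with triptans or analgesics, and Protocol 6.1 has the reason for each change in preventive treatment recorded in the CRF. This stands: the source data should allow correction. But the row as specified does not separate the two purposes.

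Last, the event may be rare. Protocol 6.2 limits the vouchers to study-specific advanced preventives, so a preventive gepant would not be paid for by that route, and Protocol 6.3.1 mentions gepants only for acute relief. Rarity would limit the effect, but the documents give no figure either way.

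**Conclusion.** The concern holds as a coding defect. SAP 18.6.2 has no class for an oral anti-CGRP used preventively, so such a record is left out of the preventive count. If the list is applied by class, which is its plain reading, the record is also counted as acute. Add-on use without stopping the index drug is not captured by the switching endpoint either.

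The consequence is confined to the acute/preventive breakdown within one exploratory endpoint. No effect on the SAP 11.2.2 model is established. No size can be given, because the documents report neither a rate of preventive gepant use nor a difference between arms; if nobody starts one, nothing changes. This is a minor point, worth correcting because the rule as stated misfiles a record that the protocol allows to occur. The conclusion assumes that preventive counts are built from the listed classes.

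**What to change.** In SAP 18.6.2:

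1. State that each medication record is classified by its recorded purpose (acute relief or prevention) first and by drug class second.
2. Add an entry under Preventive: Oral anti-CGRP (preventive use).
3. Limit the existing Acute entry to oral anti-CGRPs taken for acute relief.

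The cost is SAP wording and a change to the medication coding list, made before the analysis. No new data collection is evident. Coordinators already review all medication at the monthly visits (SAP 18.6.2), changes in concomitant medication are recorded with reasons (Protocol 7), reasons for changes in preventive treatment go into the CRF (Protocol 6.1), and acute use is in the daily eDiary (Protocol 8.1, Panel 3). The concomitant medication form is not among the protocol's appendices, so it should be confirmed that purpose can be read from it or derived from these sources. The change alters no treatment rule.
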